### 1.5.2 Outcome 2 – Comprehensive use was dependent on treatment

*Dependent variable specification:* A binary variable identifying participants that used all available functions based on their Tech arm assignment (1 = comprehensive functions user; 0 = not a comprehensive functions user).

- The definition of “comprehensiveness” was tested in two different ways:
  - **Definition 1: Based on use of all available functions:** Users were considered comprehensive functions users when they reached a threshold number of functions used based on their Tech Arm. For Lite-Tech users, this threshold was three selectable functions available—Bedside Tutorial, Dining on Demand, and To Learn. For Full-Tech users, this threshold was eight of the 10 functions available, including the three functions available to Lite-Tech users.
  - **Definition 2: Based on use of the functions available to all users:** Users were considered comprehensive functions users when they used the three functions that were available to all users.

*Statistical model:* Logistic regression model with non-interacted and interacted study arms as binomial predictors.

*Covariates:* No covariates were added to this analysis.

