3.1.1 Intervention description: Tech - Full/Lite

The Full-Tech intervention consisted of the standard build of the MyChart Bedside product as delivered from Epic and augmented by OSUWMC at the start of the study. The application was served by a *Home* landing page that displays events scheduled for the day and recent health updates and included access to 10 additional functions located in tabs along the side of the inpatient portal image:

1. *Home*: presented events scheduled for the day and data on patient vitals, including last blood pressure reading, current pulse and other patient vital signs refreshed from the Electronic Health Record (EHR) once every 5 minutesⁱ
2. *Bedside Tutorial*: tutorial materials for the use of MyChart Bedside, including an 11-minute video explaining how to use MyChart Bedside and access to PDF versions of tutorial materials
3. *Dining on Demand*: food ordering service
4. *To Learn*: educational resources for the patient based on their treatment plan
5. *Happening Soon*: a timeline for the care activities that the patient could expect for the day
6. *Taking Care of Me*: information detailing members of the patient's care team
7. *Messages*: non-urgent secure messaging with the patient's care team
8. *My Health*: recent vital signs and lab test results
9. *Notes*: write/record reminders and notes
10. *I Would Like*: non-urgent requests from pastoral care or gift shop
11. *OSU MyChart*: allowed the patient to access MyChart, including creating a new account

In addition to the *Home* landing page, the Lite-Tech version of MyChart Bedside consisted of the 3 functions: *Bedside Tutorial*, *Dining on Demand*, and *To Learn*.

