3.1.2 Intervention description: Touch - High/Low

The education and training intervention, referred to as Touch, was performed by trained Technology Navigators (TNs) who deliver training tailored to both the version of

ⁱ This function was automatic, so was not considered selectable and not included in the count of functions for either the Full- or Lite-Tech versions.

MyChart Bedside installed on their tablet (both Full- and Lite-Tech) and the perceived capacity of the patient.

Patients assigned to the Low-Touch intervention received an intervention focused on providing them with resources to conduct self-guided learning of MyChart Bedside. Specifically, TNs directed patients to the tutorial videos integrated in the MyChart Bedside application that explained the portal's functions.

In contrast, patients assigned to the High-Touch intervention would systematically review each of the functions of MyChart Bedside with the TN who would discuss how and when they are appropriately used. Patients were encouraged to use their tablet and follow along with the training as the TN moved through each function and ask the TN questions about their records during the presentation. The TNs tailored their presentation based on a patient's demonstrated knowledge of the technology to minimize patient participation burden while focusing on explaining the value of each function within the application. Patients unavailable after three intervention attempts were converted to Low-Touch.

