3.1.3 Allocation ratio

The Tech intervention contrasted two function sets—Lite-Tech (40% allocation), which was a minimalistic toolset focused on providing basic data to the patient, and Full-Tech (60% allocation), a more expansive toolset. The Touch intervention contrasted two training approaches—Low-Touch, a self-guided approach where patients could view built-in tutorials, and High-Touch (initially 50% allocation), where patients receive in-person guided training with the technology. The realized allocation ratios are presented in Table 2.

Table 2. Realized allocation ratio.

Tech Allocation	Touch Allocation		Total
	High	Low	
Full			
Frequency	624	1,523	2,147
Row %	29.1%	70.9%	100.0%
Column %	69.3%	76.5%	74.2%
Overall %	21.6%	52.7%	74.2%
Lite			
Frequency	277	468	745
Row %	37.2%	62.8%	100.0%
Column %	30.7%	23.5%	25.8%
Overall %	9.6%	16.2%	25.8%
Total			
Frequency	901	1,991	2,892
Row %	31.2%	68.8%	100.0%
Column %	100.0%	100.0%	100.0%
Overall %	31.1%	68.8%	100.0%

The assignment protocol used three phases where the Touch allocation ratio was changed by the research team.

1. In Phase 1, patients received the High-Touch intervention only after consenting to the study and submitting their Admission survey (see Section 3.8.2). Low-Touch patients could view the tutorial at any point and were not required to complete the Admission survey. Phase 1 assigned patients to High/Low-Touch in a 1:1 ratio.
2. In Phase 2, beginning in February 2018, the study shifted to a 3:1 ratio of High/Low-Touch. This change was done to ensure that sufficient individuals were assigned to the High-Touch intervention due to under-enrollment. Quality monitoring of the study found a number of exogenous factors that were impacting the High-Touch intervention, including, but not limited to: patient discharges; patient moved to other rooms; patient not present during TN rounding; patient was engaged with the care team and unable to work with the TN; and tablet returned prior to receiving an intervention. This change in the ratio was intended to increase the number of patients who would be eligible to receive a High-Touch intervention while maintaining the *per protocol* approach in that these exceptions were considered a component of the Protocol.

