### 1.5 Hypothesis 1: Inpatient portal use

*H1: Individuals assigned to the High intervention levels for Tech and Touch will demonstrate higher use of MyChart Bedside.*

We operationalized higher use in this hypothesis in three ways:

1. Frequency of use
2. Comprehensive use

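### The comprehensive-use outcome scores the Bedside Tutorial, the function to which Low-Touch patients are sent as their training, so the Touch contrast mixes training delivery with portal use, in a direction the documents do not fix.

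*SAP*

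**What the plan says.** H1 is listed with the primary outcomes (Protocol 2.2) and predicts a direction: "Individuals assigned to the High intervention levels for Tech and Touch will demonstrate higher use of MyChart Bedside" (SAP 1.5).

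SAP 1.5.2 tests H1 with a binary comprehensive-use variable, defined in two ways:

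- **Definition 1, Lite-Tech:** "this threshold was three selectable functions available", namely "Bedside Tutorial, Dining on Demand, and To Learn". All three are needed.
- **Definition 1, Full-Tech:** "this threshold was eight of the 10 functions available, including the three functions available to Lite-Tech users".
- **Definition 2, everyone:** all three shared functions must be used.

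The model is a logistic regression on Tech, Touch and their interaction, with no covariates.

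In Low-Touch, "TNs directed patients to the tutorial videos integrated in the MyChart Bedside application" (Protocol 3.1.2). Protocol 3.1.3 calls the arm "a self-guided approach where patients could view built-in tutorials". Protocol 3.1.1 describes the Bedside Tutorial function as "tutorial materials for the use of MyChart Bedside, including an 11-minute video explaining how to use MyChart Bedside", so it is the place to which Low-Touch patients are sent. In High-Touch, the navigator goes through every function with the patient, who is encouraged to follow on the tablet (Protocol 3.1.2).

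Protocol 6.3.5 maps active log actions to the 10 functions. It makes no exception for tutorial actions or for actions made during training.

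**The concern.** An outcome meant to show how fully patients use the portal should not have, as a required part, the content of one of the training arms being compared. Here a Low-Touch patient who does what the navigator suggests has met one of three conditions for success by that act. A High-Touch patient who uses Dining on Demand and To Learn but never opens the tutorial fails Definition 2 and, in Lite-Tech, also Definition 1. Conversely, a High-Touch patient who taps through every function during the walk-through may meet all the conditions in that one session.

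In both cases the Touch odds ratio reflects delivery of training as well as later use. A reader of the H1 result could not tell the two apart. The SAP plans no analysis of this outcome without the tutorial. The issue concerns the Touch contrast and is separate from the different thresholds in the two Tech arms.

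**Working it through.** The documents give no rate, effect size or power for comprehensive use, so there is no figure to reproduce. What follows is algebra plus a stated range of assumptions.

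**1. When the contrast changes sign.** For the three-function rule, P(comprehensive) = t × q. Here t is the probability of opening the tutorial, and q is the probability of using the other two functions given that it was opened. The Touch contrast reverses when t_Low / t_High exceeds q_High / q_Low. With q assumed at 0.40 High and 0.30 Low, the odds ratio on the other functions is (0.40/0.60)/(0.30/0.70) = 1.56.

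- t of 0.3 High, 0.6 Low: 0.12 v 0.18, OR = (0.12/0.88)/(0.18/0.82) = 0.62.
- t of 0.5 in both: 0.20 v 0.15, OR 1.42.
- t of 0.7 High, 0.5 Low: 0.28 v 0.15, OR = (0.28/0.72)/(0.15/0.85) = 2.20.

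**2. Spurious effect by assigned arm, with no effect on the other functions.** The SAP's main population is intention-to-treat (SAP 1.4.1), so only a fraction r of those assigned High-Touch is trained. Inputs:

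- q = 0.3 or 0.5, independent of tutorial use (assumed).
- Tutorial opening in Low-Touch and untrained patients, t0 = 0.3 or 0.5 (assumed).
- k = tutorial opening in trained patients relative to others, 0.5 to 1.5 (assumed).
- r = 0.62 or 0.41. Protocol Table 2 shows 901 High-Touch of 2,892. Because Protocol 4.3 moves untrained patients to Low-Touch, I read 901 as roughly the number trained. Assignment at 1:1 would give 1,446 High (901/1,446 = 0.62). Assignment at 3:1 would give 2,169 (901/2,169 = 0.415, entered as 0.41).

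Formulae: p0 = q·t0 and p1 = q·t0·(r·k + 1 − r). Significance uses a Wald test of the log odds ratio with ordinary standard errors, SE = √[1/(n1·p1(1−p1)) + 1/(n0·p0(1−p0))], at two-sided 0.05. Group sizes are 1,446 v 1,446 for r = 0.62 and 2,169 v 723 for r = 0.41.

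Example with q = t0 = 0.5 and r = 0.62, so p0 = 0.25:

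- k = 0.5: p1 = 0.25 × (0.31 + 0.38) = 0.1725, OR = (0.1725/0.8275)/(0.25/0.75) = 0.625.
- k = 1.5: p1 = 0.25 × (0.93 + 0.38) = 0.3275, OR = (0.3275/0.6725)/(0.25/0.75) = 1.46.

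Over all eight combinations of q, t0 and r:

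| k | Spurious OR | P(significant against High-Touch) | P(significant for High-Touch) |
|---|---|---|---|
| 0.5 | 0.625–0.78 | 0.37 to above 0.99 | about 0 |
| 0.75 | 0.80–0.89 | 0.12–0.70 | about 0 |
| 1 | 1.00 | 0.025 | 0.025 |
| 1.25 | 1.11–1.22 | about 0 | 0.11–0.65 |
| 1.5 | 1.23–1.46 | about 0 | 0.29 to above 0.99 |

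**3. Would dropping the tutorial be enough?** Not entirely, because Dining on Demand and To Learn are also shown in the walk-through. Suppose training-session taps alone raise joint use of those two by 25% in trained patients, so p1 = q(1 + 0.25r). With q = 0.3 and r = 0.41, 0.331 v 0.30 gives OR 1.15. With q = 0.5 and r = 0.62, 0.5775 v 0.50 gives OR 1.37.

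**4. Limits.** The calculation is a two-group comparison. It omits the hospital-clustered standard errors and the provisioning-length offset of SAP 1.4.2, and the interaction term. It does not model the eight-of-10 rule, which under Definition 1 applies to 2,147 of 2,892 participants (74.2%).

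**The case against.** The strongest reply concerns direction. A reader might infer that the rule is biased against High-Touch and would hide or reverse a real benefit, since patients trained in person have little reason to open a tutorial. The documents do not support that. High-Touch patients go through every function, tablet in hand, and nothing removes those actions from the outcome. Low-Touch patients are only pointed to the tutorial and need not open it. A k above 1 is therefore as compatible with the text as a k below 1. This stands, and it is why the range above covers both sides of 1.

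Three further replies have partial force:

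- **Full-Tech wording.** If the phrase about the three shared functions merely describes the 10, a Full-Tech user can reach eight without the tutorial. That weakens the point for Definition 1 in Full-Tech. It leaves Definition 2 and Lite-Tech untouched.
- **SAP 1.5.3 models use by function on Touch.** It does so in Full-Tech only, and as shares of each user's total actions. It gives a view of tutorial use but does not correct the outcome in 1.5.2, and it omits Lite-Tech, where the tutorial is one of three required functions.
- **The SAP describes analyses already performed, so replacing the definition now is post hoc.** This is fair, and it is a reason to accept a sensitivity analysis reported beside the SAP's definitions.

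The tutorial is a genuine portal function and can be reported as one. That does not justify requiring it in a comparison where one arm is directed to it.

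**Conclusion.** The structural point follows from the text alone. Under Definition 2, and under Definition 1 for Lite-Tech, success requires use of the function that constitutes Low-Touch training, and no exclusion, covariate or planned sensitivity analysis offsets this. For Full-Tech under Definition 1 the tutorial contributes to the count and is mandatory only on one reading.

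The size and sign are not established. For the three-function rule, a spurious Touch odds ratio between about 0.625 and 1.46 is possible if trained patients open the tutorial 0.5 to 1.5 times as often as others. This rests on assumed values for q, t0 and k, on an inferred r, and on independence of tutorial use from use of the other functions. At k = 1 there is no distortion. The significance probabilities rest further on ordinary standard errors. A claim that the Touch effect is in fact reversed, or that High-Touch is penalised, would go beyond the documents. The change is worth making because it is cheap and removes a component tied to the assigned training.

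**What to change.** In SAP 1.5.2, for the Touch contrast:

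1. Score comprehensive use without Bedside Tutorial. For Definition 2 and Lite-Tech Definition 1, require Dining on Demand and To Learn. For Full-Tech Definition 1, restate the threshold out of the other nine functions and give the reason for the number chosen. Make this the outcome or, at minimum, a sensitivity analysis reported beside the SAP's definitions.
2. Where the logs and recorded intervention dates allow (Protocol 6.3.10), repeat the analysis without actions from the High-Touch training session. The protocol speaks of an intervention date, so if no time is available, state how the session was identified.
3. Report Bedside Tutorial use by Touch arm separately, in both Tech arms.
4. State whether the eight functions for Full-Tech must include the three shared ones.

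The cost is SAP wording, recoding of existing log data and extra logistic model runs. The downside is that a two-function rule is easier to meet, so the event rate rises and the outcome is a less demanding measure of breadth of use.

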2.2 Objectives

The ***High Tech and High Touch (HT2): Transforming patient engagement throughout the continuum of care by engaging patients with portal technology at the bedside*** study at OSU Wexner Medical Center (OSUWMC) sought to study how the deployment of a commercial (i.e., Epic Systems) inpatient portal, MyChart Bedside, impacted identified patient outcomes. To evaluate the impact of function set and training

on inpatient (i.e., MyChart Bedside) and outpatient (i.e., MyChart) portal use, the HT2 Study²⁰ was designed as a large-scale, pragmatic randomized controlled trial across six hospitals in a healthcare system.

Using a two-by-two factorial design, HT2 simultaneously examined the effects of two approaches to portal training with two versions of the inpatient portal. HT2 was designed to test four study hypotheses:

Hypotheses related to primary outcomes:

H1: Patients assigned to the High intervention levels for Tech and Touch will demonstrate higher use of MyChart Bedside.

H2: Patients assigned to the High intervention levels for Tech and Touch will demonstrate higher levels of satisfaction with (H2a) and involvement in (H2b) their care experience.

Hypotheses related to secondary outcomes:

H3: Patients assigned to the High intervention levels for Tech and Touch will demonstrate higher rates of outpatient portal adoption (i.e., of Epic's MyChart) for those admitted without prior outpatient portal use (H3a), and higher use of MyChart for those admitted who had previously used the outpatient portal (H3b).

H4: Patients assigned to the High intervention levels for Tech and Touch will demonstrate higher levels of self-efficacy.

To prevent outcome reporting bias and data-driven analysis of results, we produced this detailed statistical analysis plan. The plan was originally developed and drafted prior to examination of the data, and in the absence of randomization knowledge. The plan has been revised as the analysis has proceeded.

Section 3: Study methods

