6.3.5 MyChart Bedside user actions

MyChart Bedside log file data included 58 total actions that a user could perform. These actions could be classified into two categories: active and passive actions. Active actions were user initiated, required user engagement, and had exclusive and reliable representation in the log file across the entire study time frame. For example, sending a message action only occurred when an individual initiated a message send in MyChart Bedside. Passive actions occurred automatically, were non-exclusive, and were unreliable. For example, every five minutes the tablet refreshed telemetry data through no action of the patient. As a result, the research team sought to identify all active actions and associated them with one of the 10 functions offered in MyChart Bedside.

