#### **1.4.3 Sub-sample analysis**

We performed sub-sample analysis on the study participants who received the Full-Tech intervention (see Equation 2). Instances where this sub-sample analysis was not conducted is noted in the description of that outcome.

Eq. 2:

$$\text{If } X_{Tech} = \text{Full; } y = X_{Touch}$$

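### Breadth of MyChart Bedside use, one of three H1 outcomes, is tested only through two yes/no cuts; the number of functions used is available and should be analysed beside them

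*SAP*

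**What the plan says.** H1 is listed among the primary-outcome hypotheses in Protocol 2.2: "H1: Patients assigned to the High intervention levels for Tech and Touch will demonstrate higher use of MyChart Bedside". SAP 1.5 tests it through three outcomes and names none of them as the single primary one:

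- 1.5.1: number of sessions, negative binomial.
- 1.5.2: comprehensive use.
- 1.5.3: each function's share of a user's actions, by Touch, Full-Tech only, fractional logistic.

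Comprehensive use is coded "1 = comprehensive functions user; 0 = not a comprehensive functions user", under two definitions.

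- Definition 1 depends on the Tech arm. "For Lite-Tech users, this threshold was three selectable functions available"; "For Full-Tech users, this threshold was eight of the 10 functions available, including the three functions available to Lite-Tech users".
- Definition 2 sets the same bar for everyone: "Users were considered comprehensive functions users when they used the three functions that were available to all users".

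The stated analysis is "Logistic regression model with non-interacted and interacted study arms as binomial predictors", with no covariates. SAP 1.4.3 adds a Touch comparison within Full-Tech: "We performed sub-sample analysis on the study participants who received the Full-Tech intervention". On the data behind the outcome, Protocol 6.3.5 says "the research team sought to identify all active actions and associated them with one of the 10 functions offered in MyChart Bedside". The number of distinct functions per patient therefore exists before any cut is applied. No analysis of that number is planned, and no reason is given for the cut at eight.

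**The concern.** Both definitions discard most of an ordered scale. A Full-Tech patient whom training moves from 2 to 7 functions changes nothing under Definition 1. A patient who goes from 0 to 2 shared functions changes nothing under Definition 2. This differs from the unequal bar between the Tech arms: it also affects the Touch comparison within Full-Tech, and Definition 2, where the bar is common.

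The other two H1 outcomes do not fill the gap. Session count measures frequency. The share of actions per function measures how use is divided, not how many functions a patient reached. SAP 1.5.2 is therefore the only test of breadth.

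Elsewhere the SAP leans towards keeping the full scale. Section 1.4.7 makes the full-scale linear model the default for Likert items, and the note to 1.4.4 fits count outcomes as counts. At stake is a real but modest training effect on breadth that goes undetected, followed by a null yes/no result being reported as no effect on breadth.

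**Working it through.** **The plan's own figure.** Protocol 3.4 gives only a planned enrollment of 3,872 and detectable changes of 2.2% to 3.8% on HCAHPS satisfaction scores. Power and baselines are not stated. With 1,936 per arm, two-sided 0.05 and 80% power, the detectable change is 3.79 points from a 75% baseline and 2.28 points from 92%. The figure is plausible but cannot be verified, and it does not concern H1.

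**Inputs from the documents.** High v Low Touch sizes are 624 v 1,523 in Full-Tech and 901 v 1,991 overall (Protocol Table 2). Alpha is 0.05 (SAP 1.1), taken as two-sided.

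**Assumptions.** The number of functions follows a beta-binomial distribution, with within-patient correlation 0.05-0.2 for ten functions and 0.1-0.3 for three. Touch multiplies the odds of exceeding every level by one common odds ratio. For the ten-function count, patients with no use are removed, as in Protocol 6.3.8; the quoted means are before that removal, which raises them by at most about 0.4. For the three shared functions, level 0 is kept, because a Full-Tech patient can use other functions and none of these. Hospital clustering is ignored throughout.

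**Formulas.**

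- Ordinal variance of the log odds ratio (Whitehead): V = 3(n1 + n2) / [n1·n2·(1 − Σp³)], where p are the pooled level proportions.
- Effect giving 80% power: log OR = (1.960 + 0.842)·√V.
- Yes/no: SE² = 1/[n1·a(1 − a)] + 1/[n2·b(1 − b)], where a and b are the Low- and High-Touch proportions at or above the cut. Power = Φ(log OR / SE − 1.960).

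**One case in full: Full-Tech, mean 5, correlation 0.1 (Σp³ = 0.0179, a = 13.84%).**

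- V = 3 × 2,147 / (624 × 1,523 × 0.9821) = 0.00690, so √V = 0.0831.
- log OR = 2.802 × 0.0831 = 0.233, OR = 1.26.
- High-Touch odds at the cut = (0.1384/0.8616) × 1.262 = 0.2027, so b = 16.86%.
- SE² = 1/181.6 + 1/87.5 = 0.00551 + 0.01143 = 0.01694, SE = 0.130.
- Power = Φ(0.233/0.130 − 1.960) = Φ(−0.17) = 43%, against 80% for the ordinal analysis.

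**Power of the cut when the ordinal analysis has 80%.**

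| 8 of 10, Full-Tech (624 v 1,523) | Power | 3 of 3 shared (901 v 1,991) | Power |
|---|---|---|---|
| mean 7 | 69% | mean 2.4 | 77% |
| mean 6 | 57-66% | mean 2.0 | 70-73% |
| mean 5 | 34-55% | mean 1.5 | 50-60% |
| mean 4 | 16-40% | mean 1.0 | 25-40% |

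To first order the relative efficiency of the cut is 3π(1 − π)/(1 − Σp³), where π is the pooled proportion at or above the cut. At π = 0.5 and Σp³ = 0.023 this is 0.75/0.977 = 0.77, and Φ(2.802 × √0.77 − 1.960) is about 69%, the best the ten-function cut does here. The group sizes cancel, so the comparison depends on the distribution far more than on the allocation.

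**Second method, indexed by the Low-Touch rate of comprehensive use.** The count is compared by a difference in means, again at 80% power.

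| Low-Touch rate | 8 of 10, Full-Tech | 3 of 3 shared, all users |
|---|---|---|
| 2% | 19-20% | 22-24% |
| 10% | 41% | 44% |
| 20% | 54% | 56-57% |
| 50% | 64-67% | 71-75% |

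**Larger effects.** Doubling the log OR in Full-Tech (1.26² = 1.59) gives the ordinal analysis about 100%, and the cut 91-100% at means 5-7 but only 54-95% at mean 4. In SD units (correlation 0.2), count v cut is 99% v 73% at 0.2 SD with a 10% Low-Touch rate, and 99% v 93% with a 30% rate. At 0.3 SD it is 100% v 97% and 100% v 100%, but a 12-point loss remains at a 5% rate.

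**Effect only at the threshold.** If training merely carries patients across the bar of eight, and the yes/no has 80% power, the count has 32-60% when those patients come from all lower levels and 8-25% when they come only from 6-7 functions.

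**The case against.** Several points weigh against the concern.

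- **Comprehensive use is a legitimate construct.** Reaching most functions is not the same question as the mean number used. This stands, and is why both definitions should remain.
- **The shape of the effect is unknown.** Protocol 3.1.2 has High-Touch trainers go through every function, which could push patients to near-complete use. The cut would then be the better test. The same section tailors training to what the patient already knows, so gains at all levels are at least as plausible. Neither shape can be assumed, which argues for reporting both analyses.
- **A common odds ratio on 0-3 may not hold.** Low-Touch patients are directed to the built-in tutorials, and Bedside Tutorial is one of the three shared functions, so the control arm is raised on one item. This stands as a caution about the model.
- **Table 2 may not show the randomised groups.** Touch was allocated 1:1 and then 3:1 in favour of High (Protocol 3.1.3), yet Table 2 has 31.2% High. Protocol 4.3 reassigns by receipt, while SAP 1.4.1 makes intention-to-treat the main population. This affects absolute power more than the comparison.
- **The study is complete.** Demoting specified outcomes now would be a post-hoc change of the kind Protocol 2.2 says the plan guards against. This stands, and no demotion is proposed.

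A reader might infer that the primary H1 test of Touch loses tens of points of power. The documents do not support that. Comprehensive use is one of three H1 outcomes, and the session count tests the same Touch contrast undichotomised. Nor is there a single cut at the top of the scale: there are two definitions, and eight of ten is high but not the maximum.

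**Conclusion.** The point holds for the breadth-of-use test within H1 and no further. SAP 1.5.2 reduces an available count to two yes/no variables, gives no reason, and leaves breadth without any analysis on its own scale.

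Under a modest shift across the whole range, the 8-of-10 cut loses roughly 11 points of power at a mean of 7 functions (80 − 69) and 40 to 64 points at a mean of 4 (80 − 40, 80 − 16). The 3-of-3 cut loses about 3 points at a mean of 2.4 and 40 to 55 at a mean of 1.0.

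These sizes rest on an assumed distribution, an assumed common odds ratio, an effect set to give the ordinal analysis 80% power, Table 2 group sizes and no clustering. The documents supply no distribution of functions used, no rate of comprehensive use and no expected Touch effect. A loss of tens of points is therefore possible but not established. It is small for larger effects unless comprehensive use is rare, and it turns into a gain if training works only at the bar. This is a cheap improvement to make, not an error that invalidates the outcome.

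**What to change.** Add to SAP 1.5.2 an analysis of the number of distinct functions used:

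- For Touch within Full-Tech, the number out of the 10 functions.
- For all arms, the number of the three shared functions (0-3), with the same Tech, Touch and interaction terms.

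Use a proportional-odds model or a binomial-count model, with the SAP's hospital-clustered errors and provisioning-length adjustment, and state how that adjustment enters. Check the common odds ratio on the 0-3 scale in view of the tutorial item.

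Keep both yes/no definitions as specified. Label the count analysis post hoc if results are already known. State that a null yes/no result alone will not be read as no effect on breadth.

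The cost is some SAP wording and two models on existing data. The downsides are one more analysis in a plan that does not adjust for multiplicity, and a common odds ratio that is slightly harder to explain than a percentage.
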